**Roles and Responsibilities:**

**Chief Investigator and Principal Investigator will have oversight of:**

Design and conduct of the study  
Preparation of protocol and revisions  
Preparation of standard operating procedures  
Organising trial management committee meetings  
Publication of study reports

**Local Lead investigators:**

In each participating centre a lead investigator will be identified, to be responsible for obtaining local ethics committee and research governance approval; the identification, recruitment, data collection and completion of CRF's, along with follow up of study participants and adherence to

study protocol. Lead investigators will be trial management committee members.

#### **Local Coordinators**

The local coordinators will aid the lead investigators.

#### **Surgical Intervention Trials Unit (SITU):**

Will be responsible for:

- Participant randomisation
- Database design
- Management of data collection
- Statistical analysis of trial data
- Providing data for regular DMC meetings
- Monitoring the trial
- Site initiation and close-out

To provide effective statistical support for clinical and pre-clinical studies, to ensure successful implementation of organ protection strategies.

To perform health economic evaluations of the proposed novel technologies to demonstrate cost-effectiveness.

#### **COPE Trials Central Manager:**

The Central Manager will be based in SITU and ensure that regulatory standards are maintained and the trial is conducted according to the principles of GCP. The Central Manager will also be responsible for:

- Organisation of trial management committee meetings
- Regular reporting to the sponsor on the progress of the clinical investigation.

#### **Trial statistician:**

Statistical design and analysis will be managed by the Surgical Intervention Trials Unit (SITU) statistician, [name], and supervised by [name].

The trial statistician is responsible for the statistical design of the trial and analysis of trial data. The trial statistician will also prepare documents for review by the DMC

#### **Consortium for Organ Preservation in Europe**

The Consortium for Organ Preservation in Europe (COPE) is the official organ task force of the European Society for Organ Transplantation (ESOT) and is funded by a European Commission

FP7 Award. The Consortium brings together academic institutions, clinical and scientific experts and SMEs from across Europe to work together on advancing organ preservation techniques.

There are currently a range of clinical and translational studies, known as Work Packages (WP), being funded by COPE with the aim of advancing and developing organ preservation technology.

#### **COPE Management Board**

The COPE Management Board will consist of the COPE coordinator, administrators, Work Package leaders and representatives from the Small and Medium Enterprises (SMEs) involved in the various COPE trials, including Organ Assist. The TMC will report to the Management Board periodically with updates on trial progress. If the COPE Management Board has concerns about the progress of the trial, the TMC will be informed of this with information about specific issues that need to be addressed. If required, the COPE Management Board can receive advice from the External Advisory Board, as described below.

The COPE coordinator and administrators are also required to periodically provide updates to the EU Scientific Officer on the progress of all Work Packages within the COPE consortium.

**Funder:**

The trial is funded within the Seventh Framework Programme (FP7) of the European Union,

FP7-HEALTH-2012-INNOVATION-1.  
http://cordis.europa.eu/home\_en.html  
(Grant number 305934 – Work Package 3, under  
the auspices of COPE [www.cope-eu.org](http://www.cope-eu.org))  
The funding agency had no role in the design of  
this study and will not have any role during its  
execution, analysis, interpretation of data or  
decision to submit results for publication.

**Conflicts of Interest**

None

**SYNOPSIS**

Study Title	'In house' Pre-implantation Oxygenated Hypothermic Machine Perfusion Reconditioning after Cold Storage versus Cold Storage alone in ECD Kidneys from Brain Dead Donors (POMP Trial)
Internal ref. no.	COPE:305934:WP3
Clinical Phase	Phase III trial
Trial Design	A multi-centre, participant-blinded, randomized, 24-month, parallel-group, prospective superiority study to compare the efficacy of brief 'in house' oxygenated hypothermic machine perfusion prior to transplantation of extended criteria donor kidneys from brain dead donors versus static cold storage alone to enhance 1 year graft survival after transplantation
Trial Participants	Donation after brain death donors, fulfilling the UNOS ECD criteria for kidney donation; adult kidney-only transplant recipients
Planned Sample Size	262 kidneys (131 kidneys in each treatment arm)
Follow-up duration	12 months
Planned Trial Period	36 months (24 month recruitment, 12 month follow-up)
Primary Objective	To compare the effect of HRMP+O 2 versus SCS on 1-year graft survival in ECD-kidneys.
Secondary Objectives	To compare graft and patient survival between SCS and short-term HRMP+O 2 . To compare the estimated GFR (eGFR) as a surrogate of kidney function between oxygenated HRMP and SCS kidneys. To compare the incidence of delayed graft function (DGF), slow graft function (SGF) and primary non-function (PNF) between oxygenated HRMP and SCS kidneys. To compare the incidence of acute rejection between oxygenated HRMP and SCS kidneys. To assess health economic implications of oxygenated HRMP in comparison to SCS kidneys.
Primary Endpoint	Graft survival at 12 months after transplantation
Secondary Endpoints	Patient and (death censored) graft survival at day 7, 3, 6 and 12 months after transplantation. eGFR defined by the MDRD equation at day 7, 3, 6 and 12 months after transplantation. DGF defined as the need for dialysis in the first 7 days after transplantation and preceding the return of kidney function. SGF based on functional DGF defined as the absence of decrease in the serum creatinine level of at least 10% per day for at least 3 consecutive days in the first 7 days after transplantation. PNF defined as the continued need for dialysis at 3 months after transplantation. Comparison of biopsy proven acute rejection between the 2 groups. Quality of life measures (EQ-5D-5L) at consent, 3 and 12 months, length of hospital stay (including ICU) and need/length for dialysis treatment.
Device Details	Kidney Assist (CE marked) Manufacturer- Organ Assist B.V The device has been in use for 4 years.

**1 ABBREVIATIONS**

AE	Adverse Event
CET	Centre of Evidence in Transplantation
CI	Chief Investigator
CIT	Cold Ischemic Time
CRF	Case Report Form
eCRF	Electronic Case Report Form
CTRG	Clinical Trials & Research Governance, University of Oxford
DBD	Donation after Brain Death
DCD	Donation after Cardiac Death
DGF	Delayed Graft Function
DMC	Data Monitoring Committee
EAB	External Advisory Board
eGFR	Estimated Glomerular Filtration Rate
ECD	Extended Criteria Donor
GCP	Good Clinical Practice
GP	General Practitioner
GS	Graft Survival
HMP	Hypothermic Machine Perfusion
HRMP	Hypothermic Reconditioning by Machine Perfusion
ICH	International Conference of Harmonisation
NHSBT	National Health Service Blood and Transplant
PI	Principal Investigator
PIL	Participant Information Leaflet
PNF	Primary Non-Function

R&D	NHS Trust Research & Development Department
REC	Research Ethics Committee
RR	Renal Resistance
SAE	Serious Adverse Event
SAP	Statistical Analysis Plan
SCD	Standard Criteria Donor
SCS	Static Cold Storage
SITU	Surgical Intervention Trials Unit
SME	Small and Medium Enterprises
SOP	Standard Operating Procedure
TMC	Trial Management Committee
UNOS	United Network of Organ Sharing

## 2 BACKGROUND AND RATIONALE

Renal transplantation remains the therapy of choice for patients with end stage renal disease. However, the number of patients waiting for a kidney graft continues to increase and far exceeds the availability of donor grafts (1-3). A large number of deceased organ transplants manifest a degree of early dysfunction leading to the clinical syndrome of Delayed Graft Function (DGF) (4,5). DGF represents a significant problem in clinical kidney transplantation affecting up to 30% of all deceased donor graft recipients (6). This has an impact on short-term management, including the requirement of hemodialysis treatment and is associated with an increased risk of acute rejection. Moreover DGF has been shown in multivariate analyses to increase the incidence of chronic nephropathy and later graft loss (4). The shortage of donor organs has led the transplant community to accept an increasing number of older and more marginal donor grafts for transplantation (7). Kidneys from these donors are particularly vulnerable for the development of DGF and have decreased long term graft survival. One important modifiable risk factor of DGF is ischemia injury sustained during organ preservation. Optimizing the preservation of grafts during the preservation phase is essential to reduce this ischemic injury. In those older and more marginal donor kidneys, an optimized preservation is therefore of even greater importance.

An international randomized controlled trial comparing Hypothermic Machine Perfusion (HMP) versus Static Cold Storage (SCS) in deceased donor kidneys demonstrated a significant reduction in the incidence of DGF as well as an improvement in 1- and 3-year graft survival (GS) by use of machine preservation (8-10). The improvement in GS was most pronounced in kidneys from extended criteria donors (ECD). ECDs were defined according to the UNOS (United Network for Organ Sharing) criteria, which include: Donor age  $\geq 60$  years, or  $\geq 50$  years with at least two of the following: history of hypertension, cerebrovascular cause of death and serum creatinine  $> 1.5$  mg/dl prior to retrieval. As shown in a subset cohort publication of this trial (5), the difference was most striking in ECD kidneys that developed DGF. Machine perfusion was clearly shown to have a protective impact on DGF and GS while Cold Ischemic Time (CIT) has been re-affirmed to be a major risk factor for DGF. During this trial, machine preservation was used during the entire preservation period; from procurement until time of transplantation and the preservation fluid was not actively oxygenated. From a logistical and technical perspective, this trial also demonstrated that it was perfectly feasible to use HMP for organ sharing within an international

organization like Eurotransplant. However it seems obvious that use of HMP only upon arrival of the kidney at the recipient center would facilitate logistics even further.

Whether HMP after initial SCS is effective remains subject of debate. Therefore, research from our group as well as others has been directed towards the possibility of reconditioning the marginal graft by short term in-house treatment immediately prior to the implantation of the graft. This novel strategy, that we termed '*Hypothermic Reconditioning by Machine Perfusion*' (HRMP), was based on the assumption that the ischemic period itself only pre-disposes the tissue to compromised resumption of cellular function upon warm reperfusion, but the major impact of actual preservation induced graft injury are only manifested after reperfusion of the kidney (11-13).

In experimental studies using isolated porcine kidneys, it has been shown that the outcome of potentially marginal grafts could be improved by post-hoc re-vitalization through HMP applied only at the end of the cold ischemia period (14). Here, transplanted kidneys showed improved kidney function after transplantation, when subjected to HRMP. An even higher, threefold increase in renal function could be measured, when HRMP kidneys had been perfused with oxygenated perfusion solution during machine perfusion rather than non-oxygenated perfusion solution. The benefit of a brief period of HMP just prior to renal transplantation was subsequently confirmed in a large animal auto-transplant model showing significantly improved renal function during one week after transplantation when compared to SCS alone (15). This study also demonstrated that HRMP after initial SCS preservation was equally effective at reducing early graft dysfunction after transplantation as the use of HMP during the entire preservation period. Various recent studies performed on either kidney or liver grafts give evidence for improved graft function after transplantation when oxygen is provided during machine perfusion (12, 17-18)

This study is a controlled, sufficiently powered, randomized multi-centre trial to evaluate the impact of end-ischemic reconditioning by oxygenated HMP after initial SCS on graft function of kidneys from extended criteria donors (ECD) after brain death (DBD).

While the overall study comparing HMP versus SCS as published by Moers et al. (8) had been statistically powered based on the assumption to detect a difference of at least 10% in

incidence of DGF; the subset analysis on ECD kidneys (as published by Treckmann et al. (5)) in itself had not been powered to detect one year graft survival differences. Nevertheless, the univariate analysis of this subset study on ECD kidneys revealed a significant impact of HMP on 1 year graft loss, 1-year graft function and incidence of PNF. Multivariate analysis demonstrated that HMP decreased DGF and one year graft loss.

The MP-Trial showed the potential impact of HMP in ECD kidneys. Moreover, pre-clinical studies using a large animal auto-transplant model indicate beneficial effects of short time HMP over SCS; therefore it is the goal of this study to validate these results in a clinical proof of concept study.

### **3 OBJECTIVES**

While the overall study comparing HMP versus SCS as published by Moers et al. (8) had been statistically powered based on the assumption to detect a difference of at least 10% in incidence of DGF; the subset analysis on ECD kidneys (as published by Treckmann et al. (5)) in itself had not been powered to detect one year graft survival differences. Nevertheless, the univariate analysis of this subset study on ECD kidneys revealed a significant impact of HMP on 1 year graft loss, 1-year graft function and incidence of PNF. Multivariate analysis demonstrated that HMP decreased DGF and one year graft loss. This study will compare SCS with a short period of oxygenated HMP after initial cold static storage using an established and certified machine perfusion device.

#### **3.1 PRIMARY OBJECTIVE**

To compare 1-year graft survival after HRMP with oxygenated perfusion solution versus SCS of ECD kidneys from DBD donors.

#### **3.2 SECONDARY OBJECTIVES**

- To compare graft and patient survival between SCS and short-term HRMP+O2.
- To compare the estimated GFR (eGFR) as a surrogate of kidney function between oxygenated HRMP and SCS kidneys.
- To compare the incidence of delayed graft function (DGF), slow graft function (SGF) and primary non-function (PNF) between oxygenated HRMP and SCS kidneys.
- To compare the incidence of acute rejection between oxygenated HRMP and SCS kidneys.

- To assess health economic implications of oxygenated HRMP in comparison to SCS kidneys.

[figure not shown]
## 4 TRIAL DESIGN

### 4.1 SUMMARY OF TRIAL DESIGN

The study will be conducted as a prospective, randomized, parallel group, single blinded, controlled, multi-centre, non-paired superiority trial; allocation will be on a 1:1 basis and an intention-to-treat method will be used to analyze the results.

After accepting the potential ECD organ for donation, kidneys will be allocated following the standard Eurotransplant/ UK-transplant allocation rules.

In a non-paired-design, each ECD kidney that has been accepted for transplantation by one of the participating centres will be randomly assigned to SCS or to SCS followed by reconditioning by end-ischemic oxygenated HMP (HRMP+O2). Randomizing kidneys after they have been accepted for transplantation avoids a potential bias that acceptance of the kidney is being influenced by the preservation modality.

[figure not shown]

If two kidneys are accepted for transplantation by the same centre the surgeon will decide which kidney to transplant first according to their local protocol.

It is not essential for both kidneys from a donor to enter the trial. If only one of the kidneys is deemed transplantable, it can still be included in the trial analysis.

Exceptionally anatomical situations may not allow connection of a kidney to the perfusion circuit. In this situation the kidney should be preserved by cold storage alone even though it was randomized to HRMP+O2.

Anticipated flow of patients through the trial is depicted below

## **4.2 PRIMARY and SECONDARY OUTCOME MEASURES**

### **4.2.1 Primary outcome measures**

The primary outcome for this study is Graft survival at 12 months after transplantation.

Reasons for choosing this primary end point are:

- Improvement of graft survival by HMP was most pronounced in kidneys from ECD in the previous publication by Treckmann et al (5).
- Definition of 1-year graft survival is clear and objective (in contrast to DGF): Is graft still functioning after one year: Y/N?
- The clinical and economic relevance of intermediate and long-term graft survival.

### **4.2.2 Secondary outcome measures**

- Patient and (death censored) graft survival at day 7, 3, 6 and 12 months after transplantation. eGFR defined by the MDRD equation at day 7, 3, 6 and 12 months after transplantation.
- DGF defined as the need for dialysis in the first 7 days after transplantation and preceding the return of kidney function.
- SGF based on functional DGF defined as the absence of decrease in the serum creatinine level of at least 10% per day for at least 3 consecutive days in the first 7 days after transplantation.
- PNF defined as the continued need for dialysis at 3 months after transplantation.
- Comparison of biopsy proven acute rejection between the 2 groups.
- Quality of life measures (EQ-5D-5L) at consent, 3 and 12 months, length of hospital stay (including ICU) and need/length for dialysis treatment

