**APPENDIX B: SCHEDULE OF PROCEDURES**

[figure not shown]
[figure not shown]
Activity	Pre-study Screening	Pre-study Baseline	During HRMP (at 15min)	During HRMP (at the end)	During surgery & before engraftment	During surgery & after engraftment (on closure)	D1	D2	D3	D4	D5	D6	D7	D14	M3	M6	M12
Informed Consent	x																
In-/Exclusion Criteria Recipient	x																
In-/Exclusion Criteria Donor		x															
Randomisation		x															
Donor Demographics		x															
Recipient Demographics		x															
Perfusion Parameters & Perfusate Samples			x	x													
Recipient Blood					x	x											
Graft biopsy						x											
Serum Creatinine							x	x	x	x	x	x	x	x	x	x	x
Dialysis requirement							x	x	x	x	x	x	x	x	x	x	x
Graft Survival							x	x	x	x	x	x	x	x	x	x	x
Recipient Survival							x	x	x	x	x	x	x	x	x	x	x
Quality of Life (EQ-5D-5L)	x														x		x

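### The SGF rule reads creatinine alone, so dialysis in days 1–7 can make a graft with little or no function score as free of SGF

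*Protocol*

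**What the plan says.** Section 4.2.2 gives the definition as "SGF based on functional DGF defined as the absence of decrease in the serum creatinine level of at least 10% per day", continuing "for at least 3 consecutive days in the first 7 days after transplantation". The Synopsis repeats it. Dialysis is not mentioned in the rule.

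Dialysis in the same week is a separate secondary endpoint: "DGF defined as the need for dialysis in the first 7 days after transplantation and preceding the return of kidney function". Section 3.2 lists the comparisons together: "To compare the incidence of delayed graft function (DGF), slow graft function (SGF) and primary non-function (PNF) between oxygenated HRMP and SCS kidneys". Nothing states whether a recipient may count under more than one of them.

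On frequency, Section 2 describes DGF as "affecting up to 30% of all deceased donor graft recipients". It adds, of older and more marginal donors, "Kidneys from these donors are particularly vulnerable for the development of DGF", but gives no rate for extended criteria donors.

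Appendix B schedules serum creatinine and "Dialysis requirement" on each of days 1 to 7.

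**The concern.** The rule is meant to detect slow recovery of the graft through the daily fall in creatinine. In a dialysed recipient that fall may come from the dialysis session. The SGF score then depends partly on when and how often the recipient was dialysed, and two identical grafts can be scored differently.

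The dialysis schedule is neither masked nor standardised by the protocol: care providers know the allocation (Section 4.4.4.4) and follow-up is by local protocol (Section 4.6). The affected recipients are also those with the worst early function, where the intervention is expected to help. If some of them are scored as free of SGF, a true difference in early dysfunction is diluted on this endpoint.

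**Working it through.** **Reading of the rule.** SGF is present when days 1–7 contain no run of three consecutive daily falls of at least 10%.

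**1. The plan's own figure.** Section 6.2: 80% vs 92%, two-sided alpha 5%, power 80%. With pooled variance, n per arm = [1.96·√(2·0.86·0.14) + 0.8416·√(0.80·0.20 + 0.92·0.08)]² / 0.12² = (0.9618 + 0.4068)² / 0.0144 ≈ 130.1, rounded up to 131, or 262 in total. This reproduces the plan. It concerns graft survival and is used here only to turn percentages into counts; the protocol states no rate or power for SGF.

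**2. A graft with no function, constant daily rise.** Assumptions, not from the protocol: creatinine rises 150 µmol/L per day, each session removes 50%, the day's sample reflects that session, and day 1 is 850. On a dialysis day the next value is (previous + 150) × 0.5; otherwise it is previous + 150.

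| Dialysis days | D1 | D2 | D3 | D4 | D5 | D6 | D7 | Longest run of falls ≥10% | Score |
|---|---|---|---|---|---|---|---|---|---|
| 2, 3, 4 | 850 | 500 | 325 | 238 | 388 | 538 | 688 | 3 | no SGF |
| 2, 4, 6 | 850 | 500 | 650 | 400 | 550 | 350 | 500 | 1 | SGF |

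The graft is the same in both rows. Only the schedule differs.

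**3. Does this depend on the chosen values?** Use a proportional rise r of 5%, 12% or 20% per day and a dialysis reduction c of 20%, 30% or 50%, again assumed. A dialysis day counts as a qualifying fall when (1 + r)(1 − c) ≤ 0.90.

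- Dialysis on three consecutive days: no SGF in 8 of 9 settings. The exception is r = 20%, c = 20%, where 1.20 × 0.80 = 0.96. Daily dialysis gives the same 8 of 9.
- A single session, or sessions on days 2, 4 and 6: SGF in all 18 settings, because creatinine rises again between sessions and the run never exceeds one.

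**4. A route needing only one session.** Take a partly recovering graft with two falls of its own of 10%.

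- With one session on day 2 (−40%): 700, 420, 378, 340, then flat. Three falls, so no SGF.
- Without dialysis: 700, 700, 630, 567, then flat. Two falls, so SGF.

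**5. How many recipients the missing rule concerns.** This takes the share with DGF as the share dialysed in week 1.

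| Assumed share dialysed | Of 131 | Of 262 |
|---|---|---|
| 20% | 26.2 | 52.4 |
| 30% (Section 2, all deceased donors) | 39.3 | 78.6 |
| 40% | 52.4 | 104.8 |

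These are recipients whose creatinine may be affected, not recipients misclassified.

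**6. Direction of the effect.** Let f be the share of dialysed recipients scored as no SGF, equal in both arms. The arm difference on the flag is (1 − f) × (difference in DGF) + (difference in slow function without dialysis). With an assumed DGF of 30% vs 20% and slow function without dialysis of 20% in both arms, this is 10 × (1 − f) points: 10 points at f = 0, and less as f grows. The protocol gives no basis for a value of f.

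**The case against.** **It could be left to the SAP.** Deriving an endpoint from laboratory values taken around dialysis is often SAP detail. Section 6.1 promises a detailed SAP, which was not available for this review, and the protocol's data schedule blocks nothing. This has weight. But the scoring rule itself is fixed in the protocol and, applied as written, gives the results in steps 2 to 4. If the SAP already has a dialysis rule, the protocol wording only needs to match it.

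**Most dialysed non-functioning grafts are still scored as SGF.** This stands. Single and alternate-day sessions did so in every setting tried. A reader might infer a large loss of power: with DGF of 30% vs 15% and slow function of 20% in both arms, power at 131 per arm would fall from 69% to 26% if half of dialysed grafts escaped the rule. Nothing in the protocol supports that share, so those figures are not estimates of what will happen here.

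**The overlap of SGF with DGF is not a contradiction.** This also stands. A reader might take "To compare the incidence of delayed graft function (DGF), slow graft function (SGF) and primary non-function (PNF" to mean three exclusive categories. Section 3.2 does not say so, and 4.2.2 presents SGF as a creatinine-based counterpart of DGF. A mandatory non-overlapping scale would be a preference. It could also mislead: if DGF is 30% vs 20% and half of the avoided DGF becomes slow function (20% vs 25%), total dysfunction is 50% vs 45%, a 5-point benefit, while SGF without dialysis shows a 5-point excess in the perfusion arm.

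**Conclusion.** The point holds as a defect in one secondary endpoint. As written, the SGF rule can score a graft with little or no function as no SGF because of dialysis, and score the same graft differently under another schedule.

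A reader might infer that up to 30% of recipients are misclassified. The documents do not support this. The 30% is a DGF figure for all deceased-donor recipients, it is not specific to extended criteria kidneys, and it describes exposure. It is not a ceiling here either, since Section 2 regards marginal kidneys as more prone to DGF; hence the assumed range of 20% to 40%, about 52 to 105 of 262. Only a subset would be misclassified, and its size cannot be derived from the protocol.

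A reader might also infer that the trial would record such grafts as having good early function. Only the SGF flag is affected. The protocol does not equate absence of SGF with good function, and these recipients are still captured as DGF.

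If the error is similar in both arms, the consequence is attenuation of the SGF comparison. The schedule results rest on the assumed rise and removal values and on samples that reflect the session; the protocol gives no sampling time relative to dialysis. Graft survival and the 131 per arm are untouched.

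**What to change.** In Section 4.2.2 and the Synopsis, state that:

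- functional DGF is scored as present in any recipient dialysed in days 1–7;
- the 10%-per-day creatinine rule is applied only to recipients not dialysed in that week.

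Report by arm how many SGF cases also had DGF, so that the SGF comparison can be read with and without dialysed recipients. Read the version without them descriptively, for the reason given in the last example under the objection.

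This concerns scoring only and has no bearing on when anyone is dialysed. It costs two sentences in the protocol, matching text in the SAP, and no new data or recipients, because Appendix B already schedules both items daily on days 1–7. The sample size does not change.

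The downside is that a recipient dialysed once, with an otherwise working graft, will count as dysfunction.
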